## Study summary

This subject-masked, non-randomised, crossover controlled non-dispensing study will compare the performance of Live Daily Disposable and Clariti 1day lenses, in a single study visit. Up to 50 subjects will be consented with the aim of completing at least 44 subjects. All subjects will first be fitted with the Live Daily Disposable lens and secondly with the Clariti 1day lens.

A summary of the study visit and procedures is provided in Table 1.

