### 1.5 **Study design**

Up to fifty participants will take part in a subject-masked, non-randomised crossover, controlled non-dispensing study, which will be controlled by cross comparison. Subjects will attend for one visit only which will last for approximately 2.0 hours. They will not be given any contact lenses to take away with them.

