### 1.6 **Statistical considerations**

The principal hypothesis to be tested in this work is that subjective scores will be similar for the two lenses. [REDACTED]

[REDACTED] such, these will

be compared using linear regression models or other parametric methods. [REDACTED]

[REDACTED]

[REDACTED] Deviations from this statistical plan will be discussed in the final report. Deviations may be necessary due to differences between the actual data distribution compared with the anticipated data distribution.

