#### 2.1.3 Inclusion criteria

Subjects will only be eligible for the study if:

1. They are of legal age (18) and capacity to volunteer.
2. They understand their rights as a research subject and are willing and able to sign a Statement of Informed Consent.
3. They are willing and able to follow the protocol.
4. They currently wear soft contact lenses, or have done so within the past two years.
5. They are expected to be able to be fitted with the study lenses within the power range available.

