### 2.5.1 Lenses

Details of the lenses are provided in Table 2. Both lenses are CE marked and will be used within the terms of their product licence. Each lens pair will be worn for approximately 15 minutes in the clinic only. Lens foils will be overlabelled so that the subject is masked to the lens brand.

	Lens 1	Lens 2
Name	Live Daily Disposable	Clariti 1day
Manufacturer	CooperVision Inc	CooperVision Inc
Material	Somofilcon A	Somofilcon A
EWC (%)	56	56
Base Curve (mm)	8.6	8.6
Diameter (mm)	14.0	14.1
Spherical powers (DS)	-1.00 to -6.00 (0.25 steps)	-1.00 to -6.00 (0.25 steps)

Table 2: study lenses.

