#### 3.2.2 Study visit

*Subjects should attend wearing their spectacles.*

They will then be required to sign an informed consent form prior to enrolment. A copy of the signed form will be issued to the subject. When the subject has signed the consent form, they are considered to be enrolled on the study.

Subjects will be instructed on the following:

1. Lens handling, application and removal, where necessary.
2. Specific study instructions, such as the importance of not using any other contact lens products.
3. General contact lens information such as the management of red eyes.

The following procedures will be performed (any ocular measurement procedures outlined below will be carried out on each eye).

1. Details of the ocular, medical and contact lens-wearing histories of the subject will be noted [REDACTED]
2. [REDACTED].
3. [REDACTED]
- [REDACTED]
- [REDACTED]
- [REDACTED]

4. [REDACTED]

[REDACTED]

5. The investigator will confirm that the subject satisfies all the inclusion and exclusion criteria. Subjects who fail to meet all the criteria at this time will usually be discontinued and replaced unless the reason is considered to be transient in which case a further visit can be scheduled.
6. The first lens pair, Live Daily Disposable, will be fitted selecting the closest available lenses for the subject based on refraction from the lens bank.
7. The subject will apply the lenses.

As soon as possible (*~1 minute after lens application*), lens fit will be assessed using the following evaluations: horizontal and vertical centration, corneal coverage and movement. Normally, for an acceptable fit, centration and movement will fall within currently accepted clinical criteria [REDACTED]

8. Distance high contrast monocular logMAR visual acuity will be recorded.
9. The subject will be asked to score the following subjective scores with reference to appropriate vertical visual analogue scales (0-100) [REDACTED]
  - Comfort
  - Vision
  - [REDACTED]
  - Overall score

10. [REDACTED]

11. Fifteen minutes after lens application, lens fit will be assessed (as above).

12. [REDACTED]

13. [REDACTED]

[REDACTED]

15. The subject will be asked to score the following subjective scores with reference to appropriate vertical visual analogue scales (0-100) [REDACTED]

- Comfort
- Vision
- Overall score

16. [REDACTED]

17. The contact lenses will be removed and discarded.

18. [REDACTED]

[REDACTED]

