19. The second lens pair, Clariti 1day, will be fitted selecting the closest available lenses for the subject based on refraction from the lens bank.

20. The same procedures will be carried out for the second lens pair (Clariti 1day) as the first lens pair, points 8 to 18 (above).

21. [REDACTED]

[REDACTED].

22. [REDACTED]

23. At the end of the visit (or if the subject is discontinued earlier in the visit) the subject's payment will be processed and the subject discharged, although they may have been asked by the investigator to attend a post-study follow-up visit. They should continue to use their lenses and solutions as advised, and seek aftercare for their contact lenses.

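### Every subject wears Live first and Clariti second, so the lens effect cannot be separated from the order effect

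*Combined protocol and SAP*

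**What the plan says.** The order is fixed for everyone. The Study summary states: "All subjects will first be fitted with the Live Daily Disposable lens and secondly with the Clariti 1day lens". The visit steps in Section 3.2.2 repeat it: "The first lens pair, Live Daily Disposable, will be fitted selecting the closest available lenses" at step 6 and "The second lens pair, Clariti 1day, will be fitted selecting the closest available lenses" at step 19, with step 20 applying the same assessments to the second pair.

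Section 1.5 describes a "subject-masked, non-randomised crossover, controlled non-dispensing study, which will be controlled by cross comparison". Section 1.6 sets the inferential aim: "The principal hypothesis to be tested in this work is that subjective scores will be similar for the two lenses". Section 1.6.1 sizes the study for equivalence testing with a margin of seven units on a 0-100 scale, and Section 1.4 names the subjective overall score as primary.

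The readable text gives no second sequence, no period term, no assumption that order has no effect, and no reason for the fixed order. Parts of Sections 1.4, 1.6 and 3.2.2 are redacted.

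**The concern.** In a crossover, order effects are controlled because some subjects receive the treatments in one order and some in the other. Here nobody has the reverse order. Every Live score is a first-period score and every Clariti score is a second-period score, so any change between the first and second wearing is counted as a lens difference.

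Such a change is plausible in this setting:

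- The outcome is a self-rating, which can drift or be re-anchored once there is a first lens to compare with.
- Subjects arrive in spectacles, and the inclusion criterion "They currently wear soft contact lenses, or have done so within the past two years" admits people who have been out of lenses for some time, so adaptation may differ between the first and second pair.
- Wear is short ("Each lens pair will be worn for approximately 15 minutes in the clinic only"), and both pairs fall within one visit of about two hours, so first-wear sensation, lens removal and fatigue all lie inside the comparison.
- Table 2 gives the two lenses the same material, water content, base curve and power range, with diameters of 14.0 and 14.1 mm. An order effect could be as large as any lens effect.

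The error can go either way. Order can make equivalent lenses fail the test. It can also offset a real difference and produce a false claim of equivalence, which is the error that an equivalence test exists to control.

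**Working it through.** **1. Identifiability.** For subject *i*, with lens effects τ and period effects π, the second score minus the first is

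d_i = (τ_Clariti − τ_Live) + (π_2 − π_1) + error.

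Both bracketed terms are constant across subjects, so the mean of d estimates only their sum. A design matrix with 44 subject columns, one lens column and one period column has 46 columns. Under the fixed order its rank is 45, because the lens and period columns are identical. With 22 subjects in each order the rank is 46 and both effects can be estimated.

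**2. The plan's sample size.** The inputs from Section 1.6.1 are SDs of 13.4, 14.1 and 13.7, a margin of 7, power 0.90 and N = 44. For paired two one-sided tests (TOST) with a true difference of zero:

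n = [(z(1−α) + z(1−β/2)) × SD / margin]²

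With α = 0.05 per side and SD 14.1: [(1.645 + 1.645) × 14.1 / 7]² = 43.9, so 44. SDs of 13.4 and 13.7 give 39.7 and 41.5. The plan's 44 is therefore reproduced by a paired TOST at α = 0.05. The printed alpha of 0.5 would give 11. The formula uses the quoted SDs as SDs of the paired difference, although the plan calls them inter-subject. Both readings are adopted below as assumptions.

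**3. Effect of an order shift.** The order effect is added to the true mean difference, and the exact TOST probability is found by integrating over the chi-square distribution of the sample SD (n = 44, 43 df). The offsets are assumed. Each range runs across SD 14.1 to 13.4.

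| Assumed order effect (units) | P(declare equivalence), identical lenses | P(declare equivalence), true difference 7, order opposing |
|---|---|---|
| 0 | 0.89-0.92 | 0.05 |
| 2 | 0.74-0.78 | 0.24-0.25 |
| 3 | 0.58-0.62 | 0.40-0.43 |
| 5 | 0.24-0.25 | 0.74-0.78 |

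The second column is power and the third is the type I error at the margin. A 1-unit effect leaves power at 0.85-0.89. Raising N narrows the interval around lens plus order and does not move it toward the lens effect.

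**4. Two randomised sequences.** With 22 subjects per order and period in the model (42 df), a constant period effect cancels. Power with identical lenses is 0.922, 0.909 and 0.889 for SDs of 13.4, 13.7 and 14.1, the same to three decimals as the fixed order with no order effect. Type I error at a true difference of 7 stays at 0.05 whatever the constant period effect. This assumes no differential carryover. The fixed order needs the absence of carryover as well, and also the absence of any period effect.

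**The case against.** The strongest reply is that this is a disclosed choice. The plan says openly that the study is non-randomised and states the order. Section 1.3 sets a modest aim, to gather short-term performance data on two lenses that the sponsor already makes, and both are CE marked. A fixed-order study with a stated limitation could serve that aim. But Sections 1.6 and 1.6.1 go further and set a similarity hypothesis with an equivalence margin, and the readable text does not limit the conclusion accordingly.

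A reason for the order, or a rest or check between lenses, may lie in redacted text or in the umbrella protocol. That could bear on how large an order effect is likely to be. It cannot make the lens effect identifiable, and no redacted model could either. Masking subjects to brand does not prevent adaptation, rating drift or fatigue.

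The size of the harm is illustrative, and this stands. Using the inter-subject SDs as paired SDs corresponds to a within-subject correlation of about 0.5. If 13.7 is the per-lens SD and the correlation is 0.8, the paired SD is 13.7 × √(2 × 0.2) = 8.7. A 2-unit order effect then lowers power only from about 1.00 to 0.98, and a 3-unit effect to 0.91. The same change raises the false-equivalence risk under a 2-unit opposing effect to 0.45, so it cuts both ways.

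The false-equivalence figures also need a true 7-unit difference opposed by order. Given how alike the lenses are in Table 2, failure of similar lenses to show equivalence may be the more relevant risk.

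**Conclusion.** The concern holds and should be fixed before the study starts, because it cannot be repaired once the data are collected. Under the fixed order the primary comparison estimates lens plus order, and the equivalence conclusion depends on an unstated assumption that order has no effect. This follows from the design alone and does not depend on any SD, alpha or effect size.

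The consequence in numbers is conditional on n = 44, a paired SD of 13.4-14.1, alpha 0.05 per side and assumed offsets of 2 to 5 units. Power for identical lenses falls from 0.89-0.92 to between 0.78 and 0.24. The false-equivalence risk at a true difference of 7 rises from 0.05 to between 0.24 and 0.78. The actual size and direction of any order effect are unknown.

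**What to change.** Randomise lens order 1:1 in blocks (Live then Clariti, or Clariti then Live). Amend the Study summary, Section 1.5 and steps 6, 19 and 20 of Section 3.2.2 to refer to the first and second assigned lens pair. In Section 1.6, specify a model with lens and period as fixed effects and subject as a random (blocking) effect, and state the assumption of no differential carryover.

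The cost is a randomisation list, the protocol wording with any ethics committee handling that the change needs, and one degree of freedom for period. The investigator must follow a per-subject order. The overlabelled foils in Section 2.5.1 already mask the brand, though the plan does not say that their labels carry allocation codes. No extra subjects, visits, lenses or procedures are needed.

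If the order cannot be changed, say in Sections 1.5 and 1.6 that the result estimates lens effect plus order effect, and drop the claim that lens equivalence is tested. That needs wording only.

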**Table 1: study summary.**

## Section 1. Overview

### 1.1 **Background**

This clinical investigation plan describes a clinical contact lens study (iteration) which will run under the umbrella protocol entitled, 'Multiple non-dispensing soft contact lens fitting studies' (C19-678) which received full ethical approval from The University of Manchester Research Ethics Committee 1 on May 20, 2021. The umbrella protocol describes a series of iterations which would recruit up to 50 subjects and compare CE marked contact lenses using routine clinical investigations at a single, non-dispensing visit and at a single study site (Carys Bannister Building, The University of Manchester). This iteration conforms to all of these requirements.

This document provides an outline of the specific details for this particular iteration.

### 1.3 **Study objectives**

CooperVision Inc. wishes to gather short-term clinical performance data for two of the soft contact lenses which they currently manufacture. This non-dispensing iteration will compare the performance of the Live Daily Disposable and Clariti 1day lenses.

### 1.4 **Study outcome measures**

The primary outcome measure for this study is the subjective overall score. Secondary measures are subjective comfort and vision. [REDACTED]

[REDACTED]

### 1.5 **Study design**

Up to fifty participants will take part in a subject-masked, non-randomised crossover, controlled non-dispensing study, which will be controlled by cross comparison. Subjects will attend for one visit only which will last for approximately 2.0 hours. They will not be given any contact lenses to take away with them.

### 1.6 **Statistical considerations**

The principal hypothesis to be tested in this work is that subjective scores will be similar for the two lenses. [REDACTED]

[REDACTED] such, these will

be compared using linear regression models or other parametric methods. [REDACTED]

[REDACTED]

[REDACTED] Deviations from this statistical plan will be discussed in the final report. Deviations may be necessary due to differences between the actual data distribution compared with the anticipated data distribution.

#### **1.6.1 Power analysis**

In a previous iteration of this study with soft spherical contact lenses, typical inter-subject standard deviation values on a 0-100 scale for comfort, vision [REDACTED] (at lens dispensing) were 13.4, 14.1 and 13.7 units, respectively. Assuming an equivalence margin of seven units and an alpha of 0.5, data from 44 subjects are required to provide power of 0.90 or greater for equivalence testing for these three parameters. To allow for any inadequate lens fits, up to 50 subjects will be recruited for this work.

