## Section 3. Subject management

### 3.1 Visit scheduling

Each subject will attend for a single study visit. Lenses will be worn for a defined period of time, with assessments occurring at various intervals, in accordance with the visit schedule detailed in this protocol. The subject will wear both of the study 'lens pairs' during the single study visit.

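### Section 1.6.1: the printed inputs do not give 44 subjects for this crossover, and even on the favourable reading the stated power of 0.90 is narrowly missed at SD 14.1

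*Combined protocol and SAP*

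**What the plan says.** Section 1.5 describes a "subject-masked, non-randomised crossover, controlled non-dispensing study, which will be controlled by cross comparison", and Section 3.1 adds: "The subject will wear both of the study 'lens pairs' during the single study visit". Each subject therefore supplies a score for both lenses, and the comparison is within subject.

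Section 1.6.1 takes its variability from a previous iteration: "typical inter-subject standard deviation values on a 0-100 scale for comfort, vision" and a third parameter whose name is redacted ("at lens dispensing) were 13.4, 14.1 and 13.7 units, respectively"). It continues: "Assuming an equivalence margin of seven units and an alpha of 0.5, data from 44 subjects are required to provide power of 0.90 or greater", and applies this to equivalence testing of all three parameters. The allowance for loss is "To allow for any inadequate lens fits, up to 50 subjects will be recruited for this work". The Study summary agrees: "Up to 50 subjects will be consented with the aim of completing at least 44 subjects".

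For the analysis, the visible part of Section 1.6 says only that scores will "be compared using linear regression models or other parametric methods"; the text around it is redacted. The visible text gives no SD of the within-subject difference, no correlation between the two lens scores, no assumed true difference and no sample-size formula.

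**The concern.** In a paired equivalence test the SD that drives power is that of the within-subject difference between lenses. If a single score has inter-subject SD σ under each lens and the two scores correlate at ρ, the difference has SD σ√(2(1 − ρ)). An inter-subject SD alone does not fix the power of this design. The printed alpha of 0.5 adds a second problem, because it is not a usable error rate for an equivalence claim.

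The principal hypothesis is that the two lenses score similarly, so the power statement tells a reader how to take an inconclusive result. If its inputs cannot be matched to its output, that reader cannot tell whether the study was too small or the lenses differed.

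**Working it through.** **Inputs from the documents.** SDs 13.4, 14.1 and 13.7; margin 7; alpha 0.5 as printed; power 0.90; 44 completers; up to 50 recruited (Section 1.6.1 and Study summary).

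**Assumptions, not in the documents.** Two one-sided tests (TOST), true difference 0 unless stated, and equal SDs under the two lenses. Alpha, where taken as 0.05, applies to each one-sided test. ρ is varied from 0.3 to 0.7.

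**Step 1. Reproduce 44.** The normal approximation for a paired TOST is n = [SD_diff × (z(1−α) + z(1−β/2)) / margin]², with z(1−β/2) = z(0.95) = 1.645 for power 0.90.

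- Printed alpha 0.5 (z = 0), SD 14.1: (14.1 × 1.645 / 7)² = 10.98, so 11 subjects.
- Alpha 0.5 split as 0.25 per side (z = 0.6745): (14.1 × 2.3195 / 7)² = 21.8, so 22 subjects.
- Alpha 0.05, quoted SD entered as the difference SD: (SD × 3.29 / 7)² = 39.7 (13.4), 41.5 (13.7) and 43.9 (14.1). The largest rounds up to 44.
- Alpha 0.025 per side, SD 14.1: 52.7, so 53 subjects.

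Of these paired calculations, only the third gives 44. Since σ√(2(1 − ρ)) = σ when ρ = 0.5, entering an inter-subject SD in this way amounts to assuming a correlation of 0.5.

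A non-paired route also gives 44. Two independent groups at alpha 0.5 need 2 × 10.98, just under 22 per group, or 44 in total.

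**Step 2. Exact power on the favourable reading.** Take the quoted figures as difference SDs with alpha 0.05. Replacing the normal approximation by the t-based calculation (integrating over the chi-square distribution of the variance, 43 degrees of freedom) gives, at n = 44:

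| SD of difference | Exact power at 44 | n for 0.90 |
|---|---|---|
| 13.4 | 0.92 | 42 |
| 13.7 | 0.91 | 43 |
| 14.1 | 0.89 | 46 |

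**Step 3. Exact power if the SDs are inter-subject.** SD 14.1, alpha 0.05:

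| Assumed ρ | SD of difference | Power at 44 | n for 0.90 |
|---|---|---|---|
| 0.3 | 16.68 | 0.73 | 63 |
| 0.4 | 15.45 | 0.81 | 55 |
| 0.5 | 14.10 | 0.89 | 46 |
| 0.6 | 12.61 | 0.95 | 37 |
| 0.7 | 10.92 | 0.99 | 28 |

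The largest difference SD that gives 0.90 at 44 is 13.89. The lowest adequate ρ for SD 14.1 is therefore 1 − (13.89 / 14.1)² / 2 = 0.515. The same formula gives 0.486 for SD 13.7 and 0.463 for SD 13.4.

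**Step 4. Unstated true difference.** For SD 14.1, n = 44 and ρ = 0.5, a true difference of 1 unit lowers power from 0.89 to 0.85, and 2 units lowers it to 0.74.

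**The case against.** The best defence is that the SDs are difference SDs with a loose label. Inter-subject could describe the spread of lens differences across subjects. The source is an earlier iteration under an umbrella protocol whose iterations compare lenses, so paired data may have existed. The match at 43.9 fits this reading, and 0.5 then looks like a misprint for 0.05. The shortfall would be one parameter at 0.89, and if all 50 recruits completed, power at SD 14.1 would be 0.93. This is a plausible reading, but the text does not establish it. It still leaves the label and alpha to be corrected, and the six extra places are reserved for inadequate fits.

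The remaining objections limit how far the point can go:

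- A reader might infer that the study is underpowered. The documents do not support that. They give no ρ, the threshold is only about 0.46 to 0.52, and Section 2.5.1 lists two lenses of the same material, water content and base curve, worn for about 15 minutes each in one visit. A correlation above 0.5 is plausible, and 44 would then be more than enough.
- A reader might infer from the independent-groups match that a parallel-group formula was used by mistake. It cannot be strictly excluded, because it uses alpha as printed. But it is not this design, and the plan treats 44 as subjects who each wear both lenses. It should not be given equal weight.
- Redacted text in Section 1.6 could hold variance assumptions. The gap in the SD sentence of Section 1.6.1 appears to cover only the third parameter's name, since three values follow.

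**Conclusion.** The point stands as a defect in the stated power calculation. As printed, the inputs of Section 1.6.1 do not give 44 for a paired equivalence test: alpha 0.5 gives 11. To reach 44 in this design, alpha must be read as 0.05 and 14.1 as the difference SD, or a correlation of 0.5 must be assumed without saying so. With a true difference of 0, that reading still misses the stated power for one of the three parameters, by about 0.01. If the SDs are inter-subject, the power at SD 14.1 depends on an unstated ρ and reaches 0.90 only from about 0.52 upward.

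It would go too far to call the target of 44 wrong; it may be adequate or generous. The visible text also does not show whether any quoted SD belongs to the primary outcome, the overall score: two belong to comfort and vision, which are secondary, and the third is redacted. The point should be corrected because the trial relies on these figures, but it is not evidence that the trial will fail.

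**What to change.** In Section 1.6.1:

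1. Correct alpha to the value used, and say that it applies to each one-sided test if that is so.
2. If the three SDs are SDs of within-subject lens differences, relabel them. If not, give the difference SD from the previous iteration or the correlation assumed.
3. State the assumed true difference.
4. Restate the power at 44 completers by exact paired TOST. On the favourable reading with a true difference of 0 this is 0.92, 0.91 and 0.89 for SD 13.4, 13.7 and 14.1. If no difference SD is available, report power over a range such as ρ 0.3 to 0.7.
5. Say which SD, if any, relates to the overall score.

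Keep the target of 44 and restate the power rather than raise the number. At SD 14.1, power of 0.90 would need 55 completers at ρ 0.4 and 63 at ρ 0.3, both above the limit of 50 in Sections 1.1 and 2.1.

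The cost is one recalculation, a few sentences and a slightly less favourable power figure. No study procedure changes.

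### Section 1.6.1 sets alpha at 0.5 for the equivalence test; the stated 44 subjects fit 0.05 per one-sided test, and 0.5 would allow a 50% false-equivalence rate at the margin

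*Combined protocol and SAP*

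**What the plan says.** Section 1.6 (Statistical considerations) makes similarity of the lenses the main question: "The principal hypothesis to be tested in this work is that subjective scores will be similar for the two lenses". Section 1.6.1 then gives the sample size basis. It quotes "typical inter-subject standard deviation values on a 0-100 scale" of 13.4, 14.1 and 13.7 from a previous iteration, for comfort, vision and a third parameter whose name is redacted. It continues: "Assuming an equivalence margin of seven units and an alpha of 0.5, data from 44 subjects are required to provide power of 0.90" or more, for equivalence testing on all three parameters. Up to 50 subjects are to be recruited to allow for inadequate lens fits, and the Study summary aims for at least 44 completers.

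No other readable text gives an alpha, a confidence level or a rule for concluding equivalence. Parts of section 1.6 are redacted, so such a rule may exist there.

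**The concern.** Alpha is the threshold for the equivalence claim, and 0.5 offers almost no protection. The critical value of a one-sided test at 0.5 is zero, so the test makes no allowance for sampling error: the observed mean difference only has to fall between −7 and +7. The planned sample size also looks far too large for so loose a test, which suggests that alpha, sample size and power do not belong together. If the figure were carried into the analysis, the main conclusion would rest on a false-equivalence rate of up to one in two at the margin. If it were silently corrected later, the choice between 0.05 per side and 0.05 split over two sides would be made after the data were available.

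**Working it through.** **Inputs from section 1.6.1.** Margin ±7 units; SDs 13.4, 13.7 and 14.1, of which the largest drives the sample size; power 0.90; stated n = 44. Under sections 1.5 and 3.1 each subject wears both lenses, so the data are paired.

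**Assumptions, because the readable text is silent.** The true difference is 0. The quoted SD is used as the SD of the paired difference. As SD(difference) = SD × √(2(1 − ρ)), this amounts to a within-subject correlation ρ of 0.5.

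**Formula.** For two one-sided tests on paired data (normal approximation), n = [SD × (z(1−α) + z(1−β/2)) / 7]². With power 0.90, β/2 = 0.05 and z(1−β/2) = 1.645.

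**Step 1: reproduce 44.** With α = 0.05 per one-sided test and SD 14.1, n = [14.1 × (1.645 + 1.645) / 7]² = 43.9, so 44. This is the stated figure.

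**Step 2: use the printed alpha.** With α = 0.5 per one-sided test, z(0.5) = 0, so n = [14.1 × 1.645 / 7]² = 10.98, so 11.

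**Step 3: other readings.**

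| Alpha per one-sided test | n, SD 13.4 | n, SD 13.7 | n, SD 14.1 | n, SD 14.1, exact t |
|---|---|---|---|---|
| 0.5 (as printed) | 10 | 11 | 11 | 11 |
| 0.25 (0.5 split over two sides) | 20 | 21 | 22 | 23 |
| 0.05 | 40 | 42 | **44** | 46 |
| 0.025 (0.05 split over two sides) | 48 | 50 | 53 | 55 |

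The first three columns of sample sizes use the normal approximation.

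**Step 4: sensitivity to the correlation.** For SD 14.1, ρ from 0 to 0.8 takes n from 88 down to 18 at alpha 0.05 per side, and from 22 down to 5 at 0.5 per side. At 0.5 per side, no non-negative correlation brings a paired calculation to 44.

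**Step 5: error rates with n = 44 and SD 14.1.** The standard error is 14.1/√44 = 2.126. At alpha 0.5 per side, equivalence is declared with probability Φ((7 − δ)/2.126) − Φ((−7 − δ)/2.126), where δ is the true difference. For δ = 8 the first term is Φ(−0.47) = 0.32 and the second is negligible.

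| True difference (units) | Alpha 0.5 per side | Alpha 0.05 per side (exact t) |
|---|---|---|
| 7 | 0.50 | 0.050 |
| 8 | 0.32 | 0.018 |
| 9 | 0.17 | 0.005 |

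If 0.5 is split over two sides, the probability at δ = 7 is 0.25.

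**Step 6: power at n = 44, δ = 0, SD 14.1.** At 0.5 per side it is 2Φ(7/2.126) − 1 = 0.999, well above the stated target. At 0.05 per side it is 0.901 by the normal approximation and 0.890 by exact t.

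**The case against.** The strongest reply is that this is a misprint, not a planned decision rule. The sample size itself identifies 0.05 as the intended value, and the 50% rate arises only if someone applies the printed figure literally. The section concerns power, and the redacted parts of section 1.6 may already state the test level and the interval. Both lenses are CE marked and worn for about 15 minutes at one visit, so safety is not affected.

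Much of this is fair. The figure is almost certainly a misprint, and the redacted text cannot be counted as missing. But redaction cannot make a legible 0.5 correct, and a different value in the hidden text would contradict it. Changing the digit alone would also leave open whether 0.05 applies to each test or is split over both. At n = 44 and SD 14.1 the exact t power is 0.89 in the first case and 0.79 in the second.

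Three qualifications stand:

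- The 50% rate and the 11 subjects assume that 0.5 applies to each one-sided test. Split over two sides, they become 25% and 22 (23 by exact t).
- The match to 44 holds under the normal approximation and the SD assumption above. Exact t needs 46.
- Two other calculations reach 44 from alpha 0.5. One is a parallel-group comparison at 0.5 per side, with 22 per arm, which contradicts the crossover. The other uses 0.25 per side with zero correlation between a subject's two scores. Neither is a credible basis for this plan.

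**Conclusion.** The concern holds. Section 1.6.1 prints a significance level that is wrong as it stands and inconsistent with the sample size and power in the same sentence. Taken per one-sided test, 0.5 gives a 50% chance of declaring equivalence at a true difference of 7 units and calls for 11 subjects. Split over two sides, it gives 25% and 22 or 23 subjects. A level of 0.05 per one-sided test reproduces 44 for the largest SD. These sample sizes assume a true difference of zero and an SD of the paired difference equal to the quoted inter-subject SD. The error rate at the margin depends on the alpha, not on those two assumptions. Because this is the only readable threshold for the principal hypothesis, it must be corrected before analysis.

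**What to change.** In section 1.6.1, replace the alpha of 0.5 with 0.05 for each of two one-sided tests. Add one sentence giving the matching rule: equivalence is concluded only if the 90% confidence interval for the mean within-subject difference between lenses lies entirely within −7 to +7 units. If the redacted part of section 1.6 already contains a rule, make the two agree.

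In the same edit, say that 44 comes from the normal approximation and that the quoted SD was used as the SD of the paired difference, if that is what was done.

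The cost is one corrected figure and one or two sentences. The recruitment ceiling of 50 need not change. If the sponsor wants 0.90 power by exact t for SD 14.1, the completion target would rise from 44 to 46, still within that ceiling.
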